### 7. STUDY-WIDE NUMBER OF SUBJECTS\*

NA

### 8. STUDY-WIDE RECRUITMENT METHODS\*

NA

### 9. STUDY TIMELINES\*

Participants will be enrolled in the study for approximately one year. All participants (n=16) are already enrolled in the study. The estimated date to complete the study data collection for this April 2024. Primary analyses are expected to be completed in September 2024.

### 10. STUDY ENDPOINTS\*

[figure not shown]
The primary outcome measures will be 1) anxiety symptom severity, 2) self-reported quality of life (QLESQ form), 3) completion rate of the METT (feasibility)

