### 4. OBJECTIVES\*

*The purpose of this study is to characterize visual system function in individuals with high trait anxiety. The fMRI portion of this study has already been conducted elsewhere. The follow up portion of the study is designed to determine if fMRI data can be used to predict future quality of life and anxiety symptoms that will be assessed at follow up. We hypothesize that visual cortex functional coupling will explain more variance in quality of life and anxiety severity at six months post-scan than prefrontal-amygdala functional coupling.*

*A subset of individuals with high trait anxiety will also complete an emotional faces task (MicroExpressions Training Task, or METT) as well as a 12-month follow up visit. This is an exploratory aim of the study to determine feasibility of the METT. We also hypothesize that individuals who complete the METT will show more improvement in anxiety symptoms at 12-months post-scan than those who do not.*

*Previously, participants in this study consented to an assessment visit, an fMRI visit, and a six month follow up data collection conducted remotely. In this initial consent form, it was mentioned that a subset of qualifying participants would be asked to complete the METT and a 12-month post-scan survey. The Pitt IRB asked us to consent these people via a separate consent form when they completed their six-month follow-up data collection.*

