### 5. BACKGROUND\*

*Individuals with high trait anxiety (HTA) have elevated fear responses to threatening situations and are more likely to react with nervousness or apprehension to a broad range of situations that may not be threatening. HTA is a stable individually differing feature and trans-diagnostic risk factor for the development of a range of chronic illnesses and conditions, most prominently mood and anxiety disorders. HTA is also associated with poor functional outcomes in psychiatric disorders, such as reduced quality of life (QoL). However, the neurobiological underpinnings of HTA remain unclear. Identification of modifiable mechanisms that underlie HTA is critical given that HTA is a behavioral marker that often precedes the onset of psychiatric disorders and is associated with significant illness burden and suffering.*

*HTA is characterized by heightened sensitivity to threat or potential threat. Because of the primacy of social visual information for humans, the anxiety literature emphasizes social stimuli such as novel faces (potential threat) and emotional faces. Individuals with anxiety disorders misattribute threat to neutral stimuli, overestimate threat, and identify faces as threatening at lower emotional expression intensities relative to individuals without HTA.*

*In the traditional, top-down anxiety model, this bias is believed to be due to incorrect stimulus contextualization, mediated by prefrontal cortex (PFC) projections to the amygdala. However, the role of both bottom-up and top-down processes in visual perception has long been recognized. Taken together, there is ample evidence for a reduced perceptual threshold in HTA that cannot be explained by the received top-down model. Rather, such findings suggest that misattribution of threat or “diminished threat selectivity” in HTA includes a bottom-up sensory mechanism.*

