## INVESTIGATOR STUDY PLAN - REQUIRED

### 11. PROCEDURES INVOLVED\*

To assess the relative contributions of fMRI data to anxiety severity and QoL longitudinally, participants will repeat QoL and anxiety measures via online forms approximately six months post-scan visit. These self-report forms assess various facets of anxiety symptoms and quality of life. These measures include the Depression, Anxiety and Stress Scale (DASS), Mood Anxiety Symptoms Questionnaire (MASQ), Perceived Stress Scale (PSS), Sensory Over Responder Scale (SOR), Somatic Symptoms Scale (SSS), Spielberger State Trait Anxiety Inventory, STAI, Quality of Life Enjoyment and Satisfaction Questionnaire- Short Form (QLESQ), Profile of Mood State Questionnaire (POMS), and an update to their medication form in case there have been any changes to their medication usage.

As an Exploratory Aim designed to test the hypothesized mechanism for altered visual processing in HTA and its relation to future clinical and functional measures, individuals with HTA will be randomly assigned to complete a visual discrimination behavioral manipulation at either 6 months post scan or 12 months post scan. The behavioral manipulation is the Micro Expressions Training Tool (METT), a visual discrimination task that will be used to determine if the visual system is a tractable target for intervention. The METT presents images of micro expressions; participants receive real-time feedback following forced choice emotional identification. The METT includes a brief pre-test, training, and then a post-test. It takes approximately 75 minutes to complete. We will collect performance data, to include accuracy and rate of training. Emotional micro expressions are subtle, involuntary expressions that communicate emotion. Facial micro expression identification is trainable and associated with social behavior and psychological well-being. We will repeat collections of self-report data in the HTA participants approximately 12 months from the initial fMRI visit via online survey. This will allow us to assess possible intervention effects on anxiety symptom severity and QoL 12 months later.

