### 13. Data Analysis and Management\*

With a maximum of five covariates (gender, age, socioeconomic status, fMRI motion parameters) of no interest and three needed terms, we will be 91% powered to detect moderate effects with  $f2 = 0.15$  and  $n=75$  (30 LTA, 15 intermediate, 30 HTA, as defined by the STAI score at initial recruitment at Pittsburgh). All regression analyses will be conducted with STAI as a continuous variable, but STAI score

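### Does the primary outcome of anxiety symptom severity need a named scale before the plan can stand?

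*Protocol*

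**What the plan says.** Protocol section 10 lists the endpoints: "The primary outcome measures will be 1) anxiety symptom severity, 2) self-reported quality of life (QLESQ form), 3) completion rate of the METT (feasibility". The QLESQ is named for quality of life; no scale, score or time point is given for anxiety.

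Section 4 gives the time point for the main hypothesis, that "visual cortex functional coupling will explain more variance in quality of life and anxiety severity at six months post-scan" than prefrontal-amygdala coupling does. It describes the target in general terms, as whether imaging can "predict future quality of life and anxiety symptoms that will be assessed at follow up".

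Section 11 lists the forms: "These measures include the Depression, Anxiety and Stress Scale (DASS), Mood Anxiety Symptoms Questionnaire (MASQ", followed by others that include the STAI. It introduces them with "These self-report forms assess various facets of anxiety symptoms and quality of life".

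Section 13 forms the sampling groups "as defined by the STAI score at initial recruitment at Pittsburgh" and adds "All regression analyses will be conducted with STAI as a continuous variable". It does not say whether that STAI is the recruitment or the follow-up score, or on which side of the model it stands. Section 5 says of high trait anxiety: "HTA is a stable individually differing feature".

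Sections 4, 11 and 13 place the METT under an exploratory aim, while section 10 lists its completion rate among the primary outcomes.

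**The concern.** A primary outcome normally comes with its instrument, and section 10 supplies one for quality of life in the same sentence. For anxiety there are at least three candidates, which section 11 itself says cover different facets. The main hypothesis is comparative, so one scale could favour visual cortex coupling and another prefrontal-amygdala coupling in the same participants.

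The STAI adds a complication. If the recruitment STAI is a predictor in every model, a six-month STAI outcome puts the same instrument on both sides and asks about change. The DASS or MASQ would ask about symptom level given trait anxiety. At stake would be which result counts as the primary anxiety finding and, if the choice were made after seeing results, the false positive rate.

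**Working it through.** **Inputs.** From section 13: n = 75, f2 = 0.15, five covariates and three further terms, stated power 91%. Assumed, because the documents do not give them: two-sided alpha 0.05; a model with five covariates, STAI and the two couplings; f2 of 0.10, 0.05 or 0 for prefrontal-amygdala coupling; correlation 0.3 between the couplings; residual correlation 0.5, 0.7 or 0.9 between two anxiety scales.

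**1. The plan's own figure.** A 1-df F test with 75 - 8 - 1 = 66 error df and noncentrality 0.15 × 75 = 11.25 has power 91.1%, which reproduces the 91%. It is the power for one coefficient on one outcome, whichever scale that outcome uses.

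**2. How often two scales disagree when nothing differs between them.** Dropping each coupling in turn and comparing the loss in R2 is the same as comparing the two squared t statistics. As a normal approximation, the t statistics are centred at √(0.15 × 75) = 3.354 for visual coupling and √(0.10 × 75) = 2.739 or √(0.05 × 75) = 1.936 for prefrontal-amygdala coupling. Their difference has SD √(2 × (1 + 0.3)) = 1.612.

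- f2 = 0.10: (3.354 - 2.739)/1.612 = 0.382, so one scale misranks the couplings with probability Φ(-0.382) = 0.35.
- f2 = 0.05: (3.354 - 1.936)/1.612 = 0.879 (unrounded), giving Φ(-0.879) = 0.19.

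A simulation of 20,000 studies per setting, with the same true effects on both scales, gives:

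| Prefrontal-amygdala f2 | One scale misranks | Two scales disagree, residual correlation 0.5 / 0.7 / 0.9 |
|---|---|---|
| 0.10 | 36% | 31% / 23% / 13% |
| 0.05 | 21% | 23% / 17% / 10% |
| 0 | 3% | 5% / 4% / 3% |

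The disagreement therefore needs no difference between the scales. It comes from comparing two R2 increments at n = 75, and it counts any difference, however small. The misranking column applies just as much to a scale named in advance.

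**3. The STAI on both sides.** With correlation r between the recruitment STAI and the outcome, a share 1 - r² of the outcome variance is left for the couplings.

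- Assumed stability 0.7 to 0.9 (STAI outcome): 1 - 0.49 = 51% down to 1 - 0.81 = 19%.
- Assumed correlation 0.3 to 0.6 (another scale): 1 - 0.09 = 91% down to 1 - 0.36 = 64%.

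A partial f2 of 0.15 is then (1 - r²) × 0.15/1.15 of total variance: 6.7% to 2.5% for the STAI, 11.9% to 8.3% for another scale. The questions differ, but an outcome adjusted for its own baseline is a standard analysis, and power at a given partial f2 is unchanged. The calculation also presumes a predictor role and a trait score. Section 13's sentence contrasts continuous use with recruitment cutoffs and settles neither side nor time point. Section 11 names an inventory with state and trait parts, and section 5's stability statement concerns the trait only.

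**4. METT status.** The exploratory aim is stated not to be designed for significance tests, and the section 10 entry is itself marked as feasibility. Moving the label changes no test, error rate or sample size.

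**The case for a change.** The best argument for a change is that the instrument of a primary outcome is part of the endpoint's definition, not analysis detail, and that the protocol recognises this by naming the QLESQ. An open choice also leaves room for selection. If any of three scales could be declared primary after results are seen, each tested at 0.05, the chance of at least one false positive lies between 5% (scales fully correlated) and 1 - 0.95³ = 14.3% (independent). Section 13 says follow-up is outstanding for only 16 participants, so many six-month scores may already exist.

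The observation itself stands: this document names no anxiety scale and does not say how the STAI enters. The selection figure is an upper bound for a practice the protocol nowhere provides for, and scales of related symptoms will not be independent. The timing point is weak, because 75 is the planned number rather than stated enrolment, and having no follow-up outstanding could include dropouts. This is also the follow-up part of a study approved at another institution in 2018; neither the parent protocol nor the figure in section 10 can be seen.

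Choosing for the sponsor would not help. The DASS anxiety score could be preferred only on the scale's name, since this protocol describes no separate score, and it may cluster at the low end in the 30 low-anxiety participants, 30/75 = 40% of the planned sample.

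**Conclusion.** The concern describes a gap correctly but does not show a fault that calls for a change. Section 10 leaves a detail open that analysts can fill sensibly: any of the collected anxiety scales at six months is a defensible outcome, the parent protocol or an analysis plan may already name one, and reporting the scales side by side would show any disagreement. The 17-31% disagreement (residual correlation 0.7-0.5, assumed prefrontal-amygdala f2 0.05-0.10) is sampling noise that naming a scale would not remove, since one pre-named scale misranks the couplings in about 21-36% of studies under the same assumptions. It falls to 3-5% if prefrontal-amygdala coupling has no effect. The STAI argument depends on a model role the protocol does not state, and leads at worst to a legitimate baseline-adjusted analysis. The METT's double status is a wording slip without numerical consequence. The conclusion would change if a document showed that the scale was chosen after its relation to the imaging data had been seen; nothing here suggests that.

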## INVESTIGATOR STUDY PLAN - REQUIRED

### 11. PROCEDURES INVOLVED\*

To assess the relative contributions of fMRI data to anxiety severity and QoL longitudinally, participants will repeat QoL and anxiety measures via online forms approximately six months post-scan visit. These self-report forms assess various facets of anxiety symptoms and quality of life. These measures include the Depression, Anxiety and Stress Scale (DASS), Mood Anxiety Symptoms Questionnaire (MASQ), Perceived Stress Scale (PSS), Sensory Over Responder Scale (SOR), Somatic Symptoms Scale (SSS), Spielberger State Trait Anxiety Inventory, STAI, Quality of Life Enjoyment and Satisfaction Questionnaire- Short Form (QLESQ), Profile of Mood State Questionnaire (POMS), and an update to their medication form in case there have been any changes to their medication usage.

As an Exploratory Aim designed to test the hypothesized mechanism for altered visual processing in HTA and its relation to future clinical and functional measures, individuals with HTA will be randomly assigned to complete a visual discrimination behavioral manipulation at either 6 months post scan or 12 months post scan. The behavioral manipulation is the Micro Expressions Training Tool (METT), a visual discrimination task that will be used to determine if the visual system is a tractable target for intervention. The METT presents images of micro expressions; participants receive real-time feedback following forced choice emotional identification. The METT includes a brief pre-test, training, and then a post-test. It takes approximately 75 minutes to complete. We will collect performance data, to include accuracy and rate of training. Emotional micro expressions are subtle, involuntary expressions that communicate emotion. Facial micro expression identification is trainable and associated with social behavior and psychological well-being. We will repeat collections of self-report data in the HTA participants approximately 12 months from the initial fMRI visit via online survey. This will allow us to assess possible intervention effects on anxiety symptom severity and QoL 12 months later.

### 12. DATA AND SPECIMEN BANKING\*

NA

### 13. Data Analysis and Management\*

With a maximum of five covariates (gender, age, socioeconomic status, fMRI motion parameters) of no interest and three needed terms, we will be 91% powered to detect moderate effects with  $f2 = 0.15$  and  $n=75$  (30 LTA, 15 intermediate, 30 HTA, as defined by the STAI score at initial recruitment at Pittsburgh). All regression analyses will be conducted with STAI as a continuous variable, but STAI score

## INVESTIGATOR STUDY PLAN - REQUIRED

*cutoffs will be used during recruitment to ensure an optimal distribution of trait anxiety. The Exploratory Aim is not designed to test for significant effects, but to provide pilot data for R01 submissions. Thus, outcome assessments will focus on effect size comparisons.*

*This submission is to complete the follow up data analyses on the outstanding 16 participants who have completed the first half of the study but not the follow up data collection. Therefore, no new participants are being recruited. Data quality will be monitored by the study PI to ensure that self-report measures are completed (unless a participant opts not to complete a measure, which is of course permissible), and that the METT is administered appropriately.*

### **14. PROVISIONS TO MONITOR THE DATA TO ENSURE THE SAFETY OF SUBJECTS\***

*Participants will be completing self-report measures of anxiety symptoms and quality of life, and some will also be completing a computerized task where they will be asked to look at emotional faces. Therefore, we do not anticipate any significant risks to the safety of participants. The data will be reviewed by the study PI, who has expertise in clinical research. This will be performed on an ongoing basis. As this study is remote, we will not be able to offer participants local resources for treatment. We will instead include a link to national resources provided by the CDC in our email communication.*

### **15. WITHDRAWAL OF SUBJECTS WITHOUT THEIR CONSENT\***

*NA*

### **16. RISKS TO SUBJECTS\***

*The most likely and common risk associated with study procedures is boredom. Participants may become bored while completing self-report forms or the METT. There is also an infrequent risk of breach of confidentiality. To minimize risk, participants will be reminded that they are free to terminate their participation at any time. Risk of breach of confidentiality will be minimized by staff training in proper procedures for handling confidential information. Furthermore, identifiable data will be kept in separate, password-protected digital files that are stored on a secure server. Self-report and METT data will be given a unique subject identifier, not identifiable information.*

### **17. POTENTIAL DIRECT BENEFITS TO SUBJECTS\***

*NA*

### **18. VULNERABLE POPULATIONS\***

*NA*

### **19. MULTI-SITE RESEARCH\***

*NA*

### **20. COMMUNITY-BASED PARTICIPATORY RESEARCH\***

*NA*

### **21. SHARING OF RESEARCH RESULTS WITH SUBJECTS\***

*We will not be sharing research results with participants.*

### **22. SETTING**

## INVESTIGATOR STUDY PLAN - REQUIRED

*Research procedures will occur in the PI's lab space in the Medical School Building. Data collection will occur via secure online form, over the phone, and/or over Zoom. These activities will be conducted in private office space over the UMass secure network.*

### 23. RESOURCES AVAILABLE

*The PI for this study is a faculty member in the Department of Psychiatry. His responsibilities include study design, training and oversight of study staff, and review of data for quality assurance. He may also participate in data collection and analysis as needed.*

*A research coordinator for this project will be primarily responsible for scheduling and reminding participants of appointments, as well as data collection and data entry. This role requires training in the use of study measures and administration of the METT behavioral task, to be provided by the PI.*

*A research assistant for this project will be responsible for cleaning, managing, organizing, and analyzing data collected for this project. This role requires training in data management and analysis, to be provided by the PI.*

*The PI is responsible for ensuring that all staff involved in this research are adequately trained and informed regarding the protocol, procedures, and their roles. This includes ongoing training in data collection and storage to ensure compliance with the IRB. The PI typically meets with study staff on a weekly basis to review study progress, but also is available as needed. New staff will be trained in all protocols and procedures, then they will observe protocols and procedures performed by the PI, then they will perform protocols and procedures with supervision by the PI before they will collect data without the PI present. These steps may be repeated at the discretion of the PI to ensure fidelity with all procedures.*

### 24. LOCAL RECRUITMENT METHODS

*The participants for this study have already been recruited and enrolled; this protocol is solely for the follow up data collection that occurs at 6 months, and, for a subset of participants with high trait anxiety, at 12 months. There are 16 remaining participants with outstanding follow up data collection.*

*Participants were recruited from the Pittsburgh, PA community via Pitt+Me, a University of Pittsburgh-based research recruitment site, as well as via community flyering. Identifiers were recorded only for the purpose of payment. Each participant was assigned a unique ID and the database containing these identifiers and that linked the unique ID to these identifiers is stored on a secure server and is password protected. Only staff involved in scheduling data collection have access to this database.*

*Payment for the six month data collection is \$15. Participants who are eligible for the 12 month data collection receive an additional \$20 for completion of surveys and an additional \$15 for completion of the METT, for a possible total of up to \$50.*

*The PI will work with UMass Chan Grant Accounting to compensate subjects during the period when BoA is being replaced.*

*A (\$15-\$50) card issued by a major bank will be given to each participant. To be eligible to receive the research stipend - the subject's name, address, phone number, and type of phone (mobile, landline) will be provided to the UMass Chan business office to procure the card. The card will be mailed directly to the subject. Once this information is provided to the business office – this identifying information will be destroyed by the PI.*

## INVESTIGATOR STUDY PLAN - REQUIRED

### 25. LOCAL NUMBER OF SUBJECTS

*There are 16 participants with outstanding follow up data collection.*

### 26. CONFIDENTIALITY

*Data will include METT outcomes (accuracy and completeness data) that will be recorded by study staff in a digital or paper format. Participant responses to survey data and medication form data will be digital. There is the potential that some data (METT outcomes, medication forms) may need to be collected in a hard copy format in case of computing difficulties. Regardless of format, all data will be coded with a unique subject ID and will not have direct identifiers.*

*Data will be collected primarily by the research coordinator but may also be collected by the PI if necessary for scheduling reasons. Data will be collected either via REDCap, or via secure servers housed at the University of Pittsburgh (we have a reliance agreement in progress for this purpose). Digital data will be stored on secure, password protected servers at UMass Chan or the University of Pittsburgh. Any hard copies will be stored in locked file cabinets in locked office space that is a part of the PI's lab space on the third floor of The Medical School Building.*

*The METT will be administered remotely via Zoom over the UMass network. This will occur with the use of a laptop and will not occur from locations outside of the PI's lab space.*

*Access will be limited to study staff or secondary investigators for related research questions. Data released to secondary investigators will be released in a de-identified format. Individuals not involved in data collection or scheduling will not have access to identifying information. Identifying information and its link to the unique subject ID will be stored in a password-protected database on a password-protected server.*

*Whenever feasible, identifiers will be removed from study-related information, and personally identifiable information is kept separate from actual data. Precautions are in place to ensure the data is secure by using passwords and encryption, etc. No identifiable data will be released to anyone without the signed consent of the participant and no identification of the subject as a participant will be made to outside sources without signed consent. We keep no detailed written narratives with private information.*

*This study was automatically assigned a certificate of confidentiality as it was funded by the NIH.*

